# 4.7.5 Follow-up- Participant Interaction #4(4-weeks Post Acupressure; Week 10, +/- 2 weeks)

Participants return to study site or we will conduct the interaction via BlueJeans or Skype. BFI, SLAQ, PROMIS Fatigue 8, RAND SF-36, PSQI, BPI, GAD7, SWLS, FM Survey Criteria, IPAQ and PANAS will be administered. Any adverse events will be collected. All participants will have the option of being taught what study investigators consider to be the most effective acupressure technique.

# 4.8 Assessment Measures.

# 4.81. Disease Activity

Systemic Lupus Activity Questionnaire (SLAQ): is a self-administered tool developed for screening and epidemiologic studies; it is not intended for clinical management or in place of physical examination. The SLAQ is based on items from a physician-scored activity index (SLAM) that are suitable for self-report. It includes 24 symptoms questions and a single numerical rating scale asking the patient to rate their disease activity over the past three months, based on their most active day during that time. While the SLAQ correlates well with physician tools, as with any measure that does not include laboratory measures, it will not detect abnormalities in laboratory findings among asymptomatic patients.

# 4.8.2 Fatigue (primary measure)

Brief Fatigue Inventory (BFI) consists of 9 items that are rated on a 0-10 rating scale where 0 represents "no fatigue or does not interfere" and 10 refers to "bad fatigue or completely interferes with activity/work." The BFI has been validated in disease groups including rheumatologic populations.

# 4.8.3 Fatigue (secondary measure)

The PROMIS Fatigue-Short Form 8 consists of 8 items that assess the impact and experience of fatigue in the past week. It uses a 5-point Likert-like scale with response options that range from "Not at all" to "Very much." A raw score is calculated by summing scores across items then a conversion table is used to calculate T-scores with higher scores indicating greater fatigue.

# 4.8.4 Health-Related Quality of Life

The Rand SF-36 is a reliable and valid self-report questionnaire consisting of 36 items aggregated to score 8 subscales related to physical and mental health. Subscales include Physical Functioning, Role Physical, Bodily Pain, General Health, Vitality, Social Function, Role Emotional and Mental Health. The subscale scores are normalized for a mean of 50 with a standard deviation of 10 where higher scores indicate better health.

# 4.8.5 Pain

The Brief Pain Inventory (BPI) is a 15-item self-report measure that has been validated for use in a wide variety of pain states. The BPI assesses for the presence of pain, pain intensity (i.e., worst, least, average, current) and functional interference from pain. Broad validation of this measure in the context of assessing chronic pain in FM has been reviewed.

## 4.8.6 Sleep

Pittsburgh Sleep Quality Index (PSQI) is a widely used, valid and reliable measure of global sleep quality and sleep-related symptoms. The 19-items yield 7 component-scores that reflect common sleep problems such as subjective sleep quality, sleep disturbance and use of sleep medication. The components are summed to yield a global score (0 to 21) with poorer sleep quality associated with a higher score.

#### 4.8.7 Depression

Patient Health Questionnaire 9-item (PHQ-9): The PHQ-9 is a 9-item multipurpose instrument that has utility for screening, diagnosing, monitoring, and measuring the severity of depression. Diagnostic validity has been assessed in studies of primary care and obstetrical clinics. Scores ≥10 have a sensitivity of 88% and a specificity of 88% for major depression. Scores of 5, 10, 15, and 20 have been associated with "mild" "moderate", "moderately severe," and "severe" classifications of depression.

#### 4.8.8 Anxiety

Generalized Anxiety Disorder 7-item (GAD-7). The GAD-7 is a 7-item measure of anxiety. It has good reliability, criterion, construct, and factorial validity. It has a sensitivity of 89% and specificity of 82% for generalized anxiety disorder. It can be completed in several minutes and administered longitudinally.

### 4.8.9 Subjective Well-Being Scores

Theory and research suggest that subjective well-being has at least three components: positive affective appraisal, negative affective appraisal, and life satisfaction. Composite scores for well-being will be calculated using scores obtained on the measures below. For each case, negative affect will be subtracted from positive affect and life satisfaction score will be added to that for a single global well-being score. Well-being scores derived in this manner have been shown to be sensitive to change.

Well-Being – Affect: Positive and Negative Affect Schedule (PANAS). The PANAS consists of two mood scales with 10-items each rated on a 5-point scale for assessing positive (e.g., inspired, strong) and negative affect (e.g., guilty, scared). Each scale has a range of 10-50 with higher scores indicating greater levels of affect. Both scales are internally consistent, uncorrelated, and stable over a 2-month time period; good convergent and discriminant validity have been demonstrated.

Well-Being – Life Satisfaction: Satisfaction with Life Scale (SWLS). The SWLS is a global measure of life satisfaction consisting of 5 items rated on a 7-point scale. The SWLS is a reliable and valid measure of life satisfaction showing large correlations with reports by family/friends of the person's life satisfaction, number of memories of satisfying experiences and other similar scales.

### 4.8.10 Fibromyalgia Survey Criteria

The regional distribution of pain can help differentiate pain due to peripheral damage or inflammation (e.g., a few discrete regions) vs that seen in centrally-mediated syndromes such as fibromyalgia. A modified version of the Wolfe Regional Pain Scale will be used that queries for the existence of pain in 19 bodily regions, using a checklist allowing for efficient scoring, along with the Wolfe Symptom Inventory (SI); a "fibromyalgianess" score can thus be calculated. The presence or absence of comorbid fibromyalgia (thought to occur in at least ~20% of SLE patients) is the largest predictor of pain, fatigue, and function in SLE; across various rheumatic

diseases, SI scores are associated with greater severity of disease (including mortality) and sociodemographic disadvantage.

# 4.8.11 Physical Activity

The International Physical Activity Questionnaire (IPAQ) assesses self-reported physical activity at 0 and 10 weeks via a validated 7-day recall measure in which time and frequency spent performing activities of different intensities are recorded and tallied.

# 4.8.12 Connective Tissue Screening Questionnaire (CSQ)

The Connective Tissue Screening Questionnaire (CSQ) is a validated self-report tool used to help identify connective tissue diseases (CTD) including SLE. The CSQ is reproducible, sensitive, and "moderately specific instrument for screening subjects with potential" CTD and is used as a first step in identifying subjects with SLE.

# **5.0 REPORTING ADVERSE EVENTS**

# 5.1 Definition

An adverse event (AE) is any condition which appears or worsens after a participant is enrolled in an investigational study. An AE does not necessarily have a causal relationship with the study agent.

# 5.2 Assessment of Relationship of AE to Treatment

The possibility that the adverse event is related to study treatment will be classified as one of the following: not related, unlikely, possible, probable, definite.

# 5.3 Study Specific Adverse Event Reporting Plan

All Serious Adverse Events that are deemed related, probably related or possibly related will be reported to the IRBMED within 7 days, as per UM IRBMED guidelines (http://med.umich.edu/irbmed/ae\_orio/ae\_report\_standard.htm).

All other non-serious, non-life-threatening adverse events will be reviewed by the PI and reported as per the following **Study Specific Adverse Event Reporting Plan:** 

Reportable Events	Timing of Report to IRBMED
Unanticipated / unexpected problem involving risks to subjects or others	Serious - within 7 days
	Non-Serious - with scheduled continuation review
Any physical, social, or psychological harm attributable to participation in this research study (e.g. an injury occurring	Serious - within 7 days

during a study visit, bruising at the site of acupressure treatment)	Non-Serious - with scheduled continuation review			
Death while on study	With scheduled continuation review			
Loss of job or insurability due to breach or revelation of research records or participation.	Within 7 days of notification			
Non-Reportable Events				
Pregnancy, or birth-related complications				

 
Hospitalizations and morbidity expected in population (e.g. surgery for removal of fibroid tumor)
 
				
• Other serious or non-serious events deemed not related or unlikely related to the research				

**Serious** = an event requiring hospitalization, permanent disability, incarceration, significant familial disruption (e.g. separation, divorce), job loss

**Non-Serious** = an event requiring some medical, psychological, psychiatric or similar attention to resolve.

**Scheduled continuation review** = renewal application.

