### 10.3.2 Study-specific DSMP

The PI will review study progress weekly with study staff, and problems with or pertaining to study subjects will be communicated immediately. The entire research team will meet monthly to review progress and any problems encountered. The PI will be notified when an AE occurs and will determine the attribution and relatedness of each adverse event. All AE must be given to the PI within 48 hours if involving a death or life threatening event, or within one week, if serious (not-life threatening/death) or non-serious.

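### Section 5.3 leaves death and life-threatening events out of its definition of Serious and gives deaths a single timing, continuation review, so the IRB deadline for the gravest events is conflicting or undefined

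*Combined protocol and SAP*

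**What the plan says.** All references are to the combined protocol and SAP.

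Section 5.3 (Study Specific Adverse Event Reporting Plan) has five parts that bear on this point.

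- **General rule:** "All Serious Adverse Events that are deemed related, probably related or possibly related will be reported to the IRBMED within 7 days". The sentence refers to the IRB's own guidelines by web link.
- **Lead-in to the table:** "All other non-serious, non-life-threatening adverse events will be reviewed by the PI and reported as per the following" the table that follows.
- **Table rows:** Unexpected problems and harms attributable to participation are each split into serious (7 days) and non-serious (continuation review). The row "Death while on study" is not split. Its only timing is scheduled continuation review, which the notes define as the "renewal application". The row "Loss of job or insurability due to breach or revelation of research records or participation" is due within 7 days of notification.
- **Non-reportable list:** This includes other events, serious or not, that are judged unrelated or unlikely to be related. It states no exception for death.
- **Definition of Serious:** "an event requiring hospitalization, permanent disability, incarceration, significant familial disruption (e.g. separation, divorce), job loss".

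Section 5.6 (Severity of AEs) has a fallback grading table for events without a CTCAE term. It puts hospitalization at grade 3, life-threatening at grade 4 and death at grade 5.

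Section 10.3.2 (Study-specific DSMP) requires that adverse events reach the PI "within 48 hours if involving a death or life threatening event, or within one week, if serious (not-life threatening/death) or non-serious". It also gives the PI the decision on relatedness.

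**The concern.** The definition of Serious decides which events get the 7-day route to the IRB, both in the split rows and, on a plain reading, in the general rule. It includes divorce and job loss but not the two outcomes that sections 5.6 and 10.3.2 rank highest. The one row that names death sends it to the slowest reporting route in the table.

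This is an operative rule that staff would follow when an event occurs. Applied literally, it can delay independent review of a study-related death, or leave staff without a deadline for a life-threatening event. What is at stake is safety oversight. The estimand, power and error rates are not affected.

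**Working it through.** The plan gives no figure to reproduce, so the check is to take each kind of event through the text of 5.3 and see what IRB deadline results.

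1. **Job loss caused by participation or by a breach of records.** The job-loss row applies: 7 days from notification.

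2. **Death, at least possibly related, with hospitalization.** Hospitalization meets the definition of Serious, so the general rule gives 7 days. The death row also applies and gives the next renewal. No text sets an order of precedence.

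3. **Death, at least possibly related, meeting no listed criterion** (for example, sudden death at home). Under the definition as written it is not Serious, so the general rule does not clearly reach it. The row on attributable harm gives 7 days only for serious events. The definition of Non-Serious, which concerns events needing attention to resolve, does not describe a death either. The one row that plainly fits is the death row: next renewal.

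4. **Life-threatening event, at least possibly related, meeting no listed criterion** (for example, treated without admission). It is not Serious as defined. The lead-in limits the table to events that are neither serious nor life-threatening, so it is outside the table's stated scope too. No deadline clearly applies.

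5. **Death judged unrelated or unlikely to be related.** The death row says report at renewal. The non-reportable list can be read as saying do not report. Which applies depends on what the word *Other* in that list refers back to.

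**Comparison of timing.** Let R be the number of days from notification of a death to the next renewal application. Under the death row the IRB hears after R days; under the job-loss row it hears within 7 days. The death can be reported later whenever R > 7. The documents do not give the renewal interval, so the excess, R − 7 days, cannot be given a value.

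**Consistency with other sections.**

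- *Section 10.3.2* has two tiers: 48 hours for death and life-threatening events, one week for everything else. Section 5.3 does not carry the upper tier into its definition of Serious. The 48-hour clock runs to the PI, and no section sets a matching clock to the IRB.
- *Section 5.6* ranks hospitalization (grade 3) below life-threatening (grade 4) and death (grade 5). In section 5.3 the grade 3 descriptor makes an event Serious, while grades 4 and 5 alone do not.
- *Within section 5.3*, the lead-in says the table is for events that are not serious and not life-threatening. Yet the table has a death row and two rows with serious entries.

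**The case against.** The strongest defence is that the text can be read sensibly.

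- **The lead-in.** Its opening, *All other*, contrasts the table with the general rule before it. Life-threatening events would then belong under the general rule, at 7 days if at least possibly related. The definition in the notes might serve only the table. This is a fair reading, and it means that no explicit later deadline exists for life-threatening events. But it has to be inferred, because the general rule names only serious events and the only definition of that term omits these.
- **The word Other.** In the non-reportable list it can mean other than the events already listed, including death. The rows would then fit together: related serious events in 7 days, remaining deaths at renewal, remaining unrelated events not at all. This is possible. However, the word could equally refer to the preceding non-reportable bullets, and the death row itself has no limit by relatedness.
- **The IRB's guidelines.** They are cited by link and may define serious events more fully. They cannot be checked here. The protocol writes its own definition and its own timing for death and does not say that the guidelines override them.
- **Low risk.** This is a 72-person pilot of self-acupressure whose listed physical risk is bruising (<1%). Deaths are unlikely, and many life-threatening events would lead to hospitalization and so count as Serious. That limits how often the gap would matter but does not remove it. The protocol has a row for deaths and, in 7.2.4, a rule for replacing participants who die.

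A reader might also infer that the one week allowed for telling the PI of a serious non-fatal event uses up the whole 7-day IRB limit. The documents do not support this. Nothing says that both clocks start at the event. The general rule applies to events already judged related, and the PI makes that judgement. The one row that states a start counts from notification. Section 10.3.2 also asks for immediate communication of problems, so the week is an outer limit.

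**Conclusion.** The inconsistency is real and should be corrected. Section 5.3 omits death and life-threatening events from Serious and gives deaths one timing with no limit by relatedness. As a result, the IRB deadline is conflicting for a related death with hospitalization and defaults to renewal for a related death without a listed criterion. For a life-threatening event without a listed criterion it is undefined. This sits badly with the urgency in 10.3.2 and the grading in 5.6.

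Two stronger statements should not be made. A reader might infer that every death goes only to continuation review. That is too strong, because a related death involving hospitalization also meets the 7-day rule. A reader might also infer that life-threatening events have a later deadline than job loss. The text gives them no clear deadline at all, which is a different fault. The comparison with job loss holds only for job loss caused by participation or a breach of records.

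The conclusion rests on reading the definition in 5.3 as governing the term Serious throughout that section, and on the cited IRB guidelines not displacing it. If either fails, the wording is still ambiguous and still needs reconciling. No delay in days is claimed, because the renewal interval is not stated.

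**What to change.** Amend section 5.3 so that its parts agree with each other and with sections 5.6 and 10.3.2:

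- State that death and life-threatening events count as Serious for IRB reporting.
- Reword the table's lead-in so that its stated scope matches its rows.
- State the scope of the death row by relatedness, and that the general 7-day rule prevails where both could apply.
- State whether the non-reportable list covers deaths judged unrelated or unlikely to be related.

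The cost is a wording amendment submitted to the IRB. The added reporting load should be negligible in a trial of this size and risk. No data collection, analysis or sample size changes.

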### 5.4 Follow-up of AEs

All AEs will be followed according to good medical practices, and documented as such.

### 5.5 AE Reporting and Data Elements

All participants will be questioned regarding adverse events during the follow up phone call and final visit. All participants will be instructed to contact the study coordinator via phone call or email at any time during the study if they have a concern.

All adverse events that occur after the informed consent is signed will be recorded on the adverse event case report form (CRF) whether or not related to study intervention.

The following information will be collected for all adverse events:

• AE reported date

- AE Verbatim Term
- CTCAE Term (v 4.03)
- Event onset date and event ended date
- Severity grade
- Attribution to study treatment (relatedness)
- Whether or not the event was reported as a Serious Adverse Event (SAE)
- Action taken with the study intervention
- Outcome of the event
- Comments

### 5.6 Severity of AEs

Severity will be graded according to NCI Common Terminology Criteria for Adverse Events (CTCAE) version 4.03. The CTCAE provides descriptive terminology and a grading scale for each adverse event listed. A copy of the CTCAE can be found at [http://ctep.cancer.gov].

AEs will be assessed according to the CTCAE grade associated with the AE term. AEs that do not have a corresponding CTCAE term will be assessed according to their impact on the participant's ability to perform daily activities as follows:

Grade	Severity	Description
1	Mild	
 
Asymptomatic or mild symptoms
 
Clinical or diagnostic observations only
 

		Intervention not needed
2	Moderate	
 
Minimal, local or non-invasive intervention indicated
 

		
 
Limiting age-appropriate instrumental activities of daily living
 

3	Severe	Medically significant but not immediately life- threatening
		
 
hospitalization or prolongation of hospitalization
 

		Disabling
		Limiting self-care activities of daily living
4	Life threatening	Life threatening consequences

		Urgent intervention needed
5	Death	Death related to Adverse Event

### 6.0 CONCOMITANT MEDICATION, EXERCISE, DIET AND SMOKING

### 6.1 Limitations on Medication, Exercise, Diet and Smoking

Concomitant prescribed medications are allowed except as listed in Exclusion Criteria. Participants will be asked to refrain from starting or stopping any new medications or supplements for the entire duration of the study. Acute medication will be allowed, defined as taking a medication for < 10 days over the course of a month with the intent to discontinue that medication.

Similarly participants will be asked to maintain their customary exercise, dietary and smoking habits during the screening, intervention and follow-up phase of the study. Participants will be asked to refrain from starting or stopping any new lifestyle modifications for the entire duration of the study.

### 6.2 Documentation of Medication

All chronic medications (prescription or OTC used for at least 14 days continuously), dietary supplements and/or herbal preparations taken by the participant during the study period will be documented on a CRF with information including:

- Type of medication
- Medication dosage/schedule
- Purpose for taking the medication, supplements or herbs (if available)

#### 7.0 OFF-STUDY CRITERIA

#### 7.1 Study Termination

The study will be terminated for an individual when a participant completes the full study, as defined as completing the week 10 visit (follow-up visit).

The Principal Investigator can decide to terminate a participant's participation in the study at any time. This decision could be based on factors such as unacceptable adverse events or for safety concerns. The reason for termination shall be documented in the case report form.

#### 7.2 Premature Removal of a Participant

#### 7.2.1 Personal reason

A participant may withdraw from the study at any time.

#### 7.2.2 Lost to follow-up

Several attempts must be made by telephone and letter to determine the circumstances for loss to follow-up, since such loss may be related to the study intervention.

### 7.2.3 New illness or Medication

Participants, who are diagnosed with a new chronic illness, start a new prescribed chronic medication (taking medication continuously for longer than 10 days) or have an increase in medication dose during the study period, will be withdrawn from the study and replaced by another participant. Participants who experience an acute illness (less than 2 weeks) e.g., a cold or receive acute medications will have these documented but will remain in the study.

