# 4.3 Randomization and Stratification.

Our randomization scheme will be created by our study statistician. Eligible patients will be randomized into one of four groups: once daily relaxing acupressure, once daily stimulating acupressure, once daily sham acupressure or usual care in a 1:1:1:1 ratio for a total of 72 participants with 18 randomized into each group.

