### 7.2.4 Death

Participants who die while on study will be replaced by another new patient.

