## 9.1 Primary and Secondary Aims

To investigate the change through time both within and between groups for fatigue (BFI), we will use linear mixed models (LMM). An advantage of LMM is that it acts as essentially an intent-to-treat (ITT) analysis as it uses all available data at each time point. For each LMM, a random subject intercept will be included to account for subject clustering; visit, group, and the interaction term (visit by group), will also be included as fixed effects. The models for BFI will be controlled for the fixed effects of any baseline variable such as age or lupus disease activity that is significantly different at baseline. Normality of the residuals derived from the LMM will be assessed using the Shapiro–Wilk test and q-q plots. For non-normal results a Box-Cox transformation will be utilized. The same methods will be employed to investigate secondary outcomes of interest pain (BPI severity sub-scale), sleep (PSQI global score) and quality of life (RAND SF-36).

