### 9.1.2 Handling Missing Data.

The linear mixed-effects framework is an intent-to-treat framework in the sense that it uses all available data at all time-points. So if there are missing outcome values in any phase due to patient dropout, the usual analysis will still be valid. If the proportion of dropouts is substantial (20% or more) in either arm, then we shall also perform a weighted analysis with weights equal to the inverse of the probability of dropout. On the other hand, missing covariate values for the subject-level information will be imputed using multiple imputation methods. All missing values will be imputed using the chained equation method. The advantage of using this technique is its flexibility in allowing different types of variables (categorical and continuous) to be imputed together without requiring any multivariate joint distributional assumption. In this method, the missing values are sequentially updated using bootstrap or Markov Chain Monte Carlo based on multiple regression models with other variables as covariates. This procedure will be carried out for a number of repetitions or cycles, thereby constructing an 'imputed' dataset. Ten such 'imputed' datasets will be used for the final analysis, a number which is considered adequate for most applications. Finally we shall combine the results from the ten regressions with the imputed data using Rubin's formula. The multiple imputation method uses the assumption that the missing-ness conforms to a *missing at random* pattern which allows missing-ness in a variable X to depend on other covariates but does not allow it to depend on X itself. All analyses will be carried out in the statistical software SAS version 9.2.

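### Section 7.2.3 withdraws and replaces randomised participants after illness or medication changes, but no section says how they are followed, analysed or counted, so the statement in 9.1.2 that drop-out leaves the analysis valid is not supported as written

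*Combined protocol and SAP*

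**What the plan says.** - **Withdrawal and replacement.** Section 7.2.3 covers a new chronic illness, a new prescribed chronic medication and a dose increase. Participants who "have an increase in medication dose during the study period, will be withdrawn from the study and replaced by another participant" leave the study, not only the acupressure. Section 7.2.4 adds: "Participants who die while on study will be replaced by another new patient". Sections 7.2.1 and 7.2.2 (personal withdrawal, loss to follow-up) mention no replacement.
- **Timing.** Consent, randomisation and baseline share one visit (section 4.7.2), so these removals generally follow randomisation.
- **Numbers.** Section 4.3 allocates 1:1:1:1 "for a total of 72 participants with 18 randomized into each group". Section 9.2 reaches 18 by inflating 15 completers for 16 to 17% drop-out.
- **Analysis.** Section 9.1 says that the mixed model "acts as essentially an intent-to-treat (ITT) analysis as it uses all available data at each time point". Section 9.1.2 repeats this sense of intent-to-treat and continues: "if there are missing outcome values in any phase due to patient dropout, the usual analysis will still be valid". It adds a weighted analysis "If the proportion of dropouts is substantial (20% or more) in either arm".
- **Missing-data assumption.** The only one stated is in the sentence beginning "The multiple imputation method uses the assumption that the missing-ness conforms to a", which goes on to name missing at random. That sentence concerns the imputation, which the section introduces for covariates and not for the BFI.

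**The concern.** New illness and medication change in lupus are plausibly tied to fatigue, which is the primary outcome. A rule that takes such participants out of the study removes later BFI scores for a reason that may be related to those scores. The plan then vouches for the analysis without giving the condition on which it depends.

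Replacement adds a second gap. The plan does not say whether the replaced person remains in the analysis, which arm the replacement joins, or who is in the numerator and denominator of the drop-out proportion. A reader cannot tell which participants enter the comparison. The person applying the 20% trigger has to choose a convention, possibly after seeing the data.

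**Working it through.** **1. The plan's own figure.** Inflating 15 completers: 15/(1 − 0.16) = 17.9, 15/(1 − 1/6) = 18.0, 15/(1 − 0.17) = 18.1. The stated 18 per arm reproduces. Drop-out is therefore already allowed for, and replacement is added with no rule linking the two.

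**2. What is lost, and when.** The schedule (section 4.6) and section 4.7 collect BFI at weeks 0, 2, 6 and 10. Concomitant medication is collected at baseline and weeks 6 and 10. On its plain reading, the all-available-data wording keeps every score already taken.
- Event found at week 10: nothing is lost.
- Event found at week 6: the week-6 BFI is kept and week 10 is lost.
- Event found earlier, through the week-2 call (4.7.3) or participant contact (5.5): week 6 and week 10 are lost.

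**3. When the validity statement holds.** A likelihood mixed model is valid if, given the modelled data (visit, group, baseline covariates that differ, and observed BFI), removal does not depend on the unseen BFI. Removal that depends on arm alone is not a violation. The reason for removal is not in the model, so the plan does not secure the condition.

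**4. Illustrative size.** The documents give no event rate. Assumptions: a fraction q = 10% or 15% removed in one arm only (about 2 or 3 of 18); removal correlated r = 0.3, 0.5 or 0.7 with the unseen BFI; intra-class correlation 0.5 (section 9.2). Section 9.2 can be read as a total variance of 4 (SD 2) or 4 + 4 = 8 (SD 2.83), so both are shown.

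Shift in the mean of those who remain: d = r × SD × φ(z)/(1 − q), where φ is the standard normal density at the cut-off z that leaves q above it. The model recovers part of d from earlier visits, each of which is shifted by 0.5d.
- Found at week 6: three earlier visits, each weighted 0.5/(1 + 2 × 0.5) = 0.25, leave 1 − 3 × 0.25 × 0.5 = 0.625 of d, at week 10. The week-6 shift is 0.
- Found before week 6: two earlier visits, each weighted 1/3, leave 1 − 2 × (1/3) × 0.5 = 2/3 of d, at week 6.

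| | q | SD 2: r = 0.3 / 0.5 / 0.7 | SD 2.83: r = 0.3 / 0.5 / 0.7 |
|---|---|---|---|
| d | 10% | 0.117 / 0.195 / 0.273 | 0.165 / 0.276 / 0.386 |
| d | 15% | 0.165 / 0.274 / 0.384 | 0.233 / 0.388 / 0.543 |
| Found at week 6: week-10 shift | 10% | 0.07 / 0.12 / 0.17 | 0.10 / 0.17 / 0.24 |
| | 15% | 0.10 / 0.17 / 0.24 | 0.15 / 0.24 / 0.34 |
| Found before week 6: week-6 shift | 10% | 0.08 / 0.13 / 0.18 | 0.11 / 0.18 / 0.26 |
| | 15% | 0.11 / 0.18 / 0.26 | 0.16 / 0.26 / 0.36 |

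Yardstick: the contrast standard error with 15 per arm is SD × √(2/15) = 0.73 or 1.03. The shifts are 0.10 to 0.35 of it. With b the shift in standard errors, a 5% two-sided test under no effect rejects with probability Φ(−1.96 + b) + Φ(−1.96 − b), which is 5.1% to 6.4%.

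Large-sample simulation agrees to within 0.01. It gives shifts within 0.01 of zero when removal is driven by the last observed BFI. If removal is alike across arms, the between-arm difference is about zero.

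**5. Counting.** Take an arm of 18 with one person removed under 7.2.3 and replaced, plus three other drop-outs. If the removed person counts, the proportion is 4/18 = 22.2%, or 4/19 = 21.1% if the replacement joins the same arm. If not, it is 3/18 = 16.7% or 3/19 = 15.8%. The 20% threshold lies between the two pairs.

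**The case against.** The case on the other side has real force.

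- **The intent-to-treat wording is hedged.** Section 9.1 says essentially, and 9.1.2 limits the sense to use of available data. This stands; the clearer target is the unconditional validity sentence.
- **A reader might infer that withdrawn participants' data are discarded, or that a week-6 BFI taken when the event comes to light is lost.** The documents do not support this, because the all-available-data wording keeps both.
- **A reader might infer that the treatment comparison is biased.** This is not shown. The illustration is an adverse case (removal in one arm only, tied to unseen scores), and planned medication changes are an exclusion criterion. Even so, the shifts are small against the standard error, in a pilot whose efficacy aims are exploratory.
- **A reader might infer that an arm with one replacement has 19 participants, or that the trigger would be missed.** The plan does not say which arm a replacement joins. Section 7.2.3 sits under premature removal, so counting the person as a drop-out is the natural reading, and that exceeds 20%. The trigger also only adds an analysis.
- **A reader might tie this to Aim 1.** That aim concerns feasibility of recruiting and conducting acupressure; attrition is not named as its measure.
- **Section 7.2.2 says of loss to follow-up "since such loss may be related to the study intervention".** That concerns a different kind of loss and is weak support here.
- **Further outcome collection could be called a design preference,** given that the protocol seeks stable background treatment (4.5.6, 6.1). Either target of estimation can be defended, but the plan must choose one, and outcomes not collected may not be recoverable.

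**Conclusion.** The point holds in limited form. With high confidence, four things are absent: outcome collection after a 7.2.3 event, a statement that replaced participants are analysed in their assigned arm, an allocation rule for replacements, and a counting rule. The validity statement in 9.1.2 is not supported as written, because it omits the missing-at-random condition for outcomes. This does not make the analysis invalid.

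Any bias is of unknown size and direction. The range of 0.07 to 0.36 BFI points rests wholly on the assumed removal rates, the removal in one arm and the assumed correlations. It falls to about zero under the conditions in the working, and an event found at week 10 costs no data. The case for change rests on the missing rules and the low cost of supplying them, not on that range.

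**What to change.** 1. **Section 7.2.3:** participants with such an event who still consent complete the BFI and secondary outcomes at the remaining scheduled contacts. Record the event and its date.
2. **Section 9.1:** analyse all randomised participants in their assigned arm, including any who are replaced. State whether the primary analysis uses data after the event, and report the other version as a sensitivity analysis.
3. **Section 9.1.2:** replace the unconditional validity sentence with the missing-at-random condition for outcomes.
4. **If replacement is kept:** state how replacements are allocated. Count 7.2.3 withdrawals and deaths as drop-outs for the 20% trigger, with everyone randomised to the arm as denominator.

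The cost is protocol wording, a few extra questionnaires at contacts that already exist (video is already allowed at weeks 6 and 10), a slightly less favourable attrition figure and a second estimate to report.

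A minor and separate point is the medication-duration wording. Section 6.1 defines acute use as under 10 days in a month with intent to discontinue, 6.2 documents continuous use of at least 14 days, and 7.2.3 acts on continuous use beyond 10 days. A 10-day course meets neither the 6.1 nor the 7.2.3 wording. These sections must be reconciled. No position is taken on the threshold or on clinical care.
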